5.3.5.12 Hospitalization or Prolonged Hospitalization

Any adverse event that results in hospitalization (i.e., inpatient admission to a hospital) or prolonged hospitalization should be documented and reported as a serious adverse event (per the definition of serious adverse event in Section 5.2.2), except as outlined below.

An event that leads to hospitalization under the following circumstances should not be reported as an adverse event or a serious adverse event:

- Planned hospitalization required by the protocol (e.g., for study drug administration, insertion of access device for study drug administration, or procedure required by the study)
- Hospitalization for a preexisting condition, provided that all of the following criteria are met:

The hospitalization was planned prior to the study or was scheduled during the study when elective surgery became necessary because of the expected normal progression of the disease

The patient has not experienced an adverse event

An event that leads to hospitalization under the following circumstances is not considered to be a serious adverse event, but should be reported as an adverse event instead:

- Hospitalization that was necessary because of patient requirement for outpatient care outside of normal outpatient clinic operating hours

5.3.5.13 Patient-Reported Outcome Data

Adverse event reports will not be derived from PRO data by the Sponsor, and safety analyses will not be performed through use of PRO data. Sites are not expected to review the PRO data for adverse events.

5.4 IMMEDIATE REPORTING REQUIREMENTS FROM INVESTIGATOR TO SPONSOR

Certain events require immediate reporting to allow the Sponsor to take appropriate measures to address potential new risks in a clinical trial. The investigator must report such events to the Sponsor immediately; under no circumstances should reporting take place more than 24 hours after the investigator learns of the event. The following is a list of events that the investigator must report to the Sponsor within 24 hours after learning of the event, regardless of relationship to study drug:

- Serious adverse events (defined in Section 5.2.2; see Section 5.4.2 for details on reporting requirements)
- Adverse events of special interest (defined in Section 5.2.3; see Section 5.4.2 for details on reporting requirements)
- Pregnancies (see Section 5.4.3 for details on reporting requirements)
- Accidental overdoses or medication errors (see Section 5.4.4 for details on reporting requirements)

The investigator must report new significant follow-up information for these events to the Sponsor immediately (i.e., no more than 24 hours after becoming aware of the information). New significant information includes the following:

- New signs or symptoms or a change in the diagnosis
- Significant new diagnostic test results
- Change in causality based on new information
- Change in the event's outcome, including recovery
- Additional narrative information on the clinical course of the event

Investigators must also comply with local requirements for reporting serious adverse events to the local health authority and IRB/EC.

5.4.2 Reporting Requirements for Serious Adverse Events and Adverse Events of Special Interest

5.4.2.1 Events That Occur prior to Study Drug Initiation

After informed consent for study entry has been obtained but prior to initiation of study drug, only serious adverse events caused by a protocol-mandated intervention should be reported. After informed consent for study re-entry has been obtained (see Section 3.1.3) but prior to initiation of study drug, only serious adverse events caused by a protocol-mandated intervention or prior study treatment should be reported. The paper Clinical Trial Serious Adverse Event/Adverse Event of Special Interest Reporting Form provided to investigators should be completed and submitted to the Sponsor or its designee immediately (i.e., no more than 24 hours after learning of the event), by faxing the form using the fax number provided below:

Region	Fax Number
North America	[contact]
Europe, Middle East, Africa, or Asia Pacific	[contact]

5.4.2.2 Events That Occur after Study Drug Initiation

After initiation of study drug following study entry or study re-entry, serious adverse events and adverse events of special interest will be reported until 8 weeks after the final dose of study drug. Investigators should record all case details that can be gathered immediately (i.e., within 24 hours after learning of the event) on the Adverse Event eCRF and submit the report via the electronic data capture (EDC) system. A report will be generated and sent to Safety Risk Management by the EDC system.

In the event that the EDC system is unavailable, the paper Clinical Trial Serious Adverse Event/Adverse Event of Special Interest Reporting Form provided to investigators should be completed and submitted to the Sponsor or its designee immediately (i.e., no more than 24 hours after learning of the event), by faxing the form using the fax number provided in Section 5.4.2.1. Once the EDC system is available, all information will need to be entered and submitted via the EDC system.

Instructions for reporting serious adverse events that occur >8 weeks after the final dose of study treatment are provided in Section 5.6.

5.4.3 Reporting Requirements for Pregnancies

5.4.3.1 Pregnancies in Female Patients

Female patients of childbearing potential will be instructed through the Informed Consent Form to immediately inform the investigator if they become pregnant during the study or within 8 weeks after the final dose of study drug or 18 weeks after final dose of study drug from Study GA39925, whichever is longer. A paper Clinical Trial Pregnancy Reporting Form should be completed and submitted to the Sponsor or its designee immediately (i.e., no more than 24 hours after learning of the pregnancy), by faxing the form using the fax number provided in Section 5.4.1. Pregnancy should not be recorded on the Adverse Event eCRF. The investigator should discontinue study drug and counsel the patient, discussing the risks of the pregnancy and the possible effects on the fetus. Monitoring of the patient should continue until conclusion of the pregnancy. Any serious adverse events associated with the pregnancy (e.g., an event in the fetus, an event in the mother during or after the pregnancy, or a congenital anomaly/birth defect in the child) should be reported on the Adverse Event eCRF. In addition, the investigator will submit a Clinical Trial Pregnancy Reporting Form when updated information on the course and outcome of the pregnancy becomes available.

5.4.3.2 Pregnancies in Female Partners of Male Patients

Male patients will be instructed through the Informed Consent Form to immediately inform the investigator if their partner becomes pregnant during the study or within 8 weeks after the final dose of study drug or 18 weeks after final dose of study drug from Study GA39925, whichever is longer. The investigator should report the pregnancy on the paper Clinical Trial Pregnancy Reporting Form and submit the form to the Sponsor or its designee immediately (i.e., no more than 24 hours after learning of the pregnancy), by faxing the form using the fax number provided in Section 5.4.1. Attempts should be made to collect and report details of the course and outcome of any pregnancy in the partner of a male patient exposed to study drug. When permitted by the site, the pregnant partner would need to sign an Authorization for Use and Disclosure of Pregnancy Health Information to allow for follow-up on her pregnancy. If the authorization has been signed, the investigator should submit a Clinical Trial Pregnancy Reporting Form with additional information on the pregnant partner and the course and outcome of the pregnancy as it becomes available. An investigator who is contacted by the male patient or his pregnant partner may provide information on the risks of the

pregnancy and the possible effects on the fetus, to support an informed decision in cooperation with the treating physician and/or obstetrician.

5.4.3.3 Congenital Anomalies/Birth Defects and Abortions

Any congenital anomaly/birth defect in a child born to a female patient exposed to study drug or the female partner of a male patient exposed to study drug should be classified as a serious adverse event, recorded on the Adverse Event eCRF, and reported to the Sponsor immediately (i.e., no more than 24 hours after learning of the event; see Section 5.4.2).

A spontaneous abortion should be classified as a serious adverse event (as the Sponsor considers abortions to be medically significant), recorded on the Adverse Event eCRF, and reported to the Sponsor immediately (i.e., no more than 24 hours after learning of the event; see Section 5.4.2).

If a therapeutic or elective abortion was performed because of an underlying maternal or embryofetal toxicity, the toxicity should be classified as a serious adverse event, recorded on the Adverse Event eCRF, and reported to the Sponsor immediately (i.e., no more than 24 hours after learning of the event; see Section 5.4.2). A therapeutic or elective abortion performed for reasons other than an underlying maternal or embryofetal toxicity is not considered an adverse event.

All abortions should be reported as pregnancy outcomes on the paper Clinical Trial Pregnancy Reporting Form.

5.4.4 Reporting Requirements for Cases of Accidental Overdose or Medication Error

Accidental overdose and medication error (hereafter collectively referred to as "special situations"), are defined as follows:

- Accidental overdose: accidental administration of a drug in a quantity that is higher than the assigned dose
- Medication error: accidental deviation in the administration of a drug

In some cases, a medication error may be intercepted prior to administration of the drug.

Special situations are not in themselves adverse events, but may result in adverse events. Each adverse event associated with a special situation should be recorded separately on the Adverse Event eCRF. If the associated adverse event fulfills seriousness criteria or qualifies as an adverse event of special interest, the event should be reported to the Sponsor immediately (i.e., no more than 24 hours after learning of the event; see Section 5.4.2). For efmarodocokin alfa, adverse events associated with special situations should be recorded as described below for each situation:

- Accidental overdose: Enter the adverse event term. Check the "Accidental overdose" and "Medication error" boxes.
- Medication error that does not qualify as an overdose: Enter the adverse event term. Check the "Medication error" box.
- Medication error that qualifies as an overdose: Enter the adverse event term. Check the "Accidental overdose" and "Medication error" boxes.

In addition, all special situations associated with efmarodocokin alfa, regardless of whether they result in an adverse event, should be recorded on the Adverse Event eCRF and reported to the Sponsor immediately (i.e., no more than 24 hours after learning of the event). Special situations should be recorded as described below:

- Accidental overdose: Enter the drug name and "accidental overdose" as the event term. Check the "Accidental overdose" and "Medication error" boxes.
- Medication error that does not qualify as an overdose: Enter the name of the drug administered and a description of the error (e.g., wrong dose administered, wrong dosing schedule, incorrect route of administration, wrong drug, expired drug administered) as the event term. Check the "Medication error" box.
- Medication error that qualifies as an overdose: Enter the drug name and "accidental overdose" as the event term. Check the "Accidental overdose" and "Medication error" boxes. Enter a description of the error in the additional case details.
- Intercepted medication error: Enter the drug name and "intercepted medication error" as the event term. Check the "Medication error" box. Enter a description of the error in the additional case details.

As an example, an accidental overdose that resulted in a headache would require the two entries on the Adverse Event eCRF, one entry to report the accidental overdose and one entry to report the headache. The "Accidental overdose" and "Medication error" boxes would need to be checked for both entries.

5.5 FOLLOW-UP OF PATIENTS AFTER ADVERSE EVENTS

5.5.1 Investigator Follow-Up

The investigator should follow each adverse event until the event has resolved to baseline grade or better, the event is assessed as stable by the investigator, the patient is lost to follow-up, or the patient withdraws consent. Every effort should be made to follow all

serious adverse events considered to be related to study drug or trial-related procedures until a final outcome can be reported.

During the study period, resolution of adverse events (with dates) should be documented on the Adverse Event eCRF and in the patient's medical record to facilitate source data verification.

All pregnancies reported during the study should be followed until pregnancy outcome.

5.5.2 Sponsor Follow-Up

For serious adverse events, adverse events of special interest, and pregnancies, the Sponsor or a designee may follow up by telephone, fax, email, and/or a monitoring visit to obtain additional case details and outcome information (e.g., from hospital discharge summaries, consultant reports, autopsy reports) in order to perform an independent medical assessment of the reported case.

5.6 ADVERSE EVENTS THAT OCCUR AFTER THE ADVERSE EVENT REPORTING PERIOD

The Sponsor should be notified if the investigator becomes aware of any serious adverse event that occurs after the end of the adverse event reporting period (defined as 8 weeks after the final dose of study drug), if the event is believed to be related to prior study drug treatment. These events should be reported through use of the Adverse Event eCRF. However, if the EDC system is not available, the investigator should report these events directly to the Sponsor or its designee, by faxing the paper Clinical Trial Serious Adverse Event/Adverse Event of Special Interest Reporting Form using the fax number provided to investigators.

5.7 EXPEDITED REPORTING TO HEALTH AUTHORITIES, INVESTIGATORS, INSTITUTIONAL REVIEW BOARDS, AND ETHICS COMMITTEES

The Sponsor will promptly evaluate all serious adverse events and adverse events of special interest against cumulative product experience to identify and expeditiously communicate possible new safety findings to investigators, IRBs, ECs, and applicable health authorities based on applicable legislation.

To determine reporting requirements for single adverse event cases, the Sponsor will assess the expectedness of these events *through the use of the reference safety information in the document listed below:*

Drug	Document
Efmarodocokin alfa	Efmarodocokin Alfa Investigator's Brochure

The Sponsor will compare the severity of each event and the cumulative event frequency reported for the study with the severity and frequency reported in the applicable reference document.

Reporting requirements will also be based on the investigator's assessment of causality and seriousness, with allowance for upgrading by the Sponsor as needed.

Currently there are no expected serious adverse drug reactions for efmarodocokin alfa described in the Efmarodocokin Alfa Investigator's Brochure. Thus, any treatment-emergent serious adverse event deemed related to efmarodocokin alfa will be reported as a suspected unexpected serious adverse reaction (SUSAR). Reporting of individual SUSARs to investigators, IRBs, ECs, and applicable health authorities will be done in accordance with applicable legislation.

For the purpose of SUSAR reporting, the version of the Efmarodocokin Alfa Investigator's Brochure valid at the time the SUSAR occurs will apply. SUSARs will be kept blinded unless required for medical safety reasons and/or country regulatory reasons. Unblinding to study personnel and Genentech study team members will be documented.

Six-month SUSAR reports related to efmarodocokin alfa will be provided as per local regulatory requirements. If a significant safety issue arises altering the benefit-risk profile of efmarodocokin alfa, the investigators, IRBs, ECs, and applicable health authorities will be informed prior to the next update of the Efmarodocokin Alfa Investigator's Brochure, in accordance with applicable legislation.

6. STATISTICAL CONSIDERATIONS AND ANALYSIS PLAN

Data collected from the final visit of the parent study will serve as baseline (Study Week 0) data for the extension study.

Participation during Year 2 is not required for patients who completed the study through Week 52 (Year 1) prior to the implementation of Protocol Version 6, and those who do not participate will be considered to have completed the study per protocol, provided required safety follow-up assessments have been completed.

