2. OBJECTIVES AND ENDPOINTS

This study will evaluate the long-term safety and tolerability of efmarodocokin alfa in patients with moderate to severe UC or CD. In addition, the study will obtain long-term data on the efficacy, immunogenicity, and exposure of efmarodocokin alfa. Specific objectives and corresponding endpoints for the study are outlined below. For endpoint determination, endoscopic scores will be based on interpretation by a central reader.

In this protocol, "study drug" refers to efmarodocokin alfa.

Table 1 Objectives and Corresponding Endpoints

Safety Objective	Corresponding Endpoints
• To evaluate the safety and tolerability of efmarodocokin alfa	
• Occurrence and severity of adverse events, with severity determined according to NCI CTCAE scale• Change in targeted vital signs, physical findings, and clinical laboratory test results during and following efmarodocokin alfa administration
Exploratory Efficacy Objective	Corresponding Endpoints
• To evaluate the efficacy of efmarodocokin alfa	
• Clinical response ^a at Weeks 28, 52, 80, and 104• Clinical remission ^b at Weeks 28, 52, 80, and 104• Durability of clinical remission, defined as time from achieving clinical remission ^b to loss of clinical remission ^b• Change from baseline (i.e., either the baseline score in the parent study or the last score prior to initiation of the most recent course ^c of efmarodocokin alfa during the extension study, whichever score is the most recent) in PRO2 in patients with Crohn's disease
Exploratory Pharmacokinetic Objective	Corresponding Endpoints
• To evaluate potential relationships between long-term drug exposure and the safety and efficacy of efmarodocokin alfa	
• Relationship between serum concentration or PK parameters for efmarodocokin alfa and exploratory efficacy endpoints• Relationship between serum concentration or PK parameters for efmarodocokin alfa and safety endpoints
Exploratory Immunogenicity Objective	Corresponding Endpoint
• To evaluate the immune response to efmarodocokin alfa	
• Presence of ADAs to efmarodocokin alfa during the study relative to the presence of ADAs at baseline (Study Week 0)
Exploratory Biomarker Objective	Corresponding Endpoint

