3.1.2 Efmarodocokin Alfa Administration

Patients enrolled in the extension study will receive efmarodocokin alfa treatment or undergo observation for up to approximately 2 years (through Week 104), as determined on the basis of the patient's disease status, as outlined in [Table 2](#). Upon entry into the extension study, patients will receive efmarodocokin alfa 60 µg/kg IV Q4W or undergo observation, depending on their disease status at the time of their last endoscopy in the parent study. The first dose of efmarodocokin alfa in the extension study may not be administered less than 2 weeks after last dose of study drug in parent study. During the extension study, patients will receive efmarodocokin alfa 60 µg/kg IV Q4W or undergo observation, depending on their disease status at a scheduled visit or a disease evaluation visit (details on disease evaluation visits are provided in [Section 3.1.5](#)).

Table 2 Efmardocokin Alfa Treatment Algorithm

Patient's Disease Status	Action to Be Taken
Meets criteria for clinical remission ^a	
Discontinue efmardocokin alfa (if applicable)Undergo observation and assessments per schedule of activities (see Appendix 1)
Does not meet criteria for clinical remission ^a	
Receive efmardocokin alfa 60 µg/kg IV Q4W until clinical remission is achieved ^bUndergo assessments per schedule of activities (see Appendix 1)
Meets criteria for disease flare ^c (off treatment) after entry into study	
Consult with Medical Monitor to determine appropriate course of action prior to administration of efmardocokin alfa (if applicable)
Experiences disease worsening as a result of efmardocokin alfa treatment, in the investigator's judgment, or disease flare while receiving efmardocokin alfa ^c	
Permanently discontinue efmardocokin alfaInitiate rescue therapy at discretion of investigatorUndergo safety follow-up assessments 8 weeks after final dose of efmardocokin alfa ^d

Q4W=every 4 weeks.

^a Clinical remission during the extension study, as defined in Section [3.1.4.3](#).

^b First dose of efmardocokin alfa in the extension study to be administered no less than 2 weeks after last dose of study drug in parent study

^c Disease flare during the extension study, as defined in Section [3.1.4.4](#).

^d See Section [3.1.6](#) and [Appendix 1](#) for details regarding safety follow-up.

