3.3 RATIONALE FOR STUDY DESIGN

3.3.1 Rationale for Efmarodocokin Alfa Dose and Schedule

The dose regimen of efmarodocokin alfa 60 µg/kg IV Q4W was selected on the basis of an integrated analysis of the clinical, PK, and PD data from the completed Phase Ia study (GA29468) and data from the Phase Ib study (GA29469). The 60 µg/kg IV Q4W regimen would provide a preliminary assessment of the benefit-risk of a treat-to-remission strategy to help inform the Phase III studies. The 60 µg/kg Q4W regimen enables drug exposure within the tolerable exposure range to evaluate whether efmarodocokin alfa is safe and efficacious in patients with UC or CD.

The dose regimen tested in Study GA40209 is similar to the highest dose regimen tested in the Phase II parent study GA39925 (90 µg/kg IV Q4W in the first 8 weeks of treatment and 60 µg/kg IV Q8W during the 4-month maintenance phase). The benefit-risk profile of the 60 µg/kg IV Q4W regimen is anticipated to be similar to this regimen with a 33% lower C_{max} (60 µg/kg IV Q4W vs. 90 µg/kg IV Q8W, respectively) during the first 8 weeks, but 2 times higher exposure over the subsequent 4 months (60 µg/kg IV Q4W vs. 60 µg/kg IV Q8W, respectively). The dose regimen in Study GA40209 may be adjusted on the basis of emerging data from the parent study GA39925 as described above.

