4.5 STUDY ASSESSMENTS

The schedule of activities to be performed during the study is provided in [Appendix 1](#). All activities must be performed and documented for each patient.

Data collected from the final visit of the parent study will serve as Study Week 0 (initial visit) data for the extension study. Procedures and assessments that were performed at the final visit of the parent study do not need to be repeated at Study Week 0, with the exception of the ADA sample. A baseline ADA sample should be collected at baseline (Study Week 0).

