Dose dependent increases in fibrinogen have been observed following efmarodocokin alfa treatment in the nonclinical studies with cynomolgus monkeys and in the Phase I studies (GA29468 and GA29469) which included HVs, patients with UC, and patients with CD. These increases in fibrinogen were considered on-target effects of IL-22 signaling, with peak mean cohort values within 2-fold of baseline. The fibrinogen increases were not accompanied by changes in other clotting parameters measured (prothrombin time, activated partial thromboplastin time, and internal normalized

ratio), or by clinical signs or adverse events of clotting/coagulation abnormalities. As of the data cutoff of 05 February 2021 in the ongoing blinded Phase II Study GA39925, there has been 1 serious adverse event of deep venous thrombosis in 1 patient (out of 161 patients enrolled) that was considered unrelated to the study drug/placebo by the investigator. In a preliminary data analysis from the Phase II Study GA42969 in patients with severe COVID-19 pneumonia, the number of thrombotic or embolic adverse events were comparable between efmarodocokin alfa, comparator, and placebo arms.

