6.2 SUMMARIES OF CONDUCT OF STUDY

The numbers of patients who enroll, discontinue, or complete the study will be summarized. Reasons for premature study withdrawal will be listed and summarized. Eligibility and other major protocol deviations will be listed and evaluated for their potential effects on the interpretation of study results.

Patients who withdraw from the study, irrespective of final outcome, will be considered as non-responders at analysis. All patients who received efmarodocokin alfa in this study will be pooled for analysis. Further subgroup analysis by dose change during the study or baseline characteristics may be performed if the sample size per subgroup is sufficient.

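### Change in fibrinogen and CRP from the last parent-study visit may understate the drug effect, because previously treated and never-exposed patients are pooled

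*Combined protocol and SAP*

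**What the plan says.** - **Reference value.** Section 6: "Data collected from the final visit of the parent study will serve as baseline (Study Week 0) data for the extension study". The synopsis and Appendix 1 (footnote a) say the same. Section 4.5 adds: "Procedures and assessments that were performed at the final visit of the parent study do not need to be repeated at Study Week 0". The ADA sample is the only exception.
- **Endpoint.** Section 2, Table 1 lists under safety: "Change in targeted vital signs, physical findings, and clinical laboratory test results during and following efmarodocokin alfa administration". It names no reference of its own, so the general baseline rule applies. Fibrinogen (in the coagulation panel) and CRP are study laboratory tests (Section 4.5.6).
- **Pooling.** Section 6.2: "All patients who received efmarodocokin alfa in this study will be pooled for analysis". Subgroups by dose change or baseline characteristics are optional. Section 6.4 breaks safety down by dose and infusions received, not by parent treatment.
- **Who is pooled.** Section 1.3 admits efmarodocokin alfa responders and non-responders as well as vedolizumab and placebo patients.
- **Drug effect.** Section 5.1.1.5: "Dose dependent increases in fibrinogen have been observed following efmarodocokin alfa treatment". Section 1.2.2 reports dose-dependent rises in CRP.
- **Contrast.** Response and PRO2 have their own baseline rule (Sections 3.1.4.2 and 6.5), under which the parent-study baseline can be used. Laboratory change has no such route to a pre-exposure value.

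**The concern.** For a never-exposed patient, change from Week 0 measures the rise on the drug. For a patient treated in the parent study, it measures that rise less whatever effect was still present at the last parent visit. Averaging the two gives a quantity that depends on the mix of prior treatments and on washout, as well as on the drug.

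This matters because safety is the purpose of the study and no formal testing is planned, so the descriptive displays are the result. Fibrinogen is the laboratory marker behind the clotting risk described in Section 5.1.1.5. A blunted pooled rise could be read as reassurance.

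**Working it through.** **The plan's own figures.** Section 6.1 gives intervals for 135 patients (0.5 × 270) and no figure for laboratory change. The intervals reproduce:
- Remission 20%, Wald: 0.20 ± 1.96 × √(0.2 × 0.8/135) = 0.20 ± 0.0675, or 13.3% to 26.7%, as stated.
- Serious adverse events, Clopper-Pearson: 9/135 gives 3.1% to 12.3% and 18/135 gives 8.1% to 20.3%, matching the stated 3% to 12% and 8% to 20%.

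None of these depends on the laboratory baseline.

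**Is residual effect at Week 0 plausible?**
- Non-responders may leave GA39925 from Week 8 (Section 4.1.1.1), and Section 6.1 expects about 135 non-responders from that study.
- Section 3.3.1 describes the highest GA39925 regimen as 90 µg/kg "IV Q4W in the first 8 weeks of treatment". A patient dosed on that schedule would reach Week 8 no more than about 4 weeks after a dose (an inference). The next sentence of Section 3.3.1 gives the 90 µg/kg interval as Q8W, under which the gap could be up to 8 weeks. The two statements must be reconciled before residual exposure can be judged.
- The documents do not give the actual interval from last parent dose to final parent visit, the fibrinogen time course, or the mix of parent arms.

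**Pooled change.** Let
- U = mean level without drug,
- E = mean true rise above U at an extension visit, assumed equal in both groups,
- f = share of the pool given efmarodocokin alfa in the parent study,
- r = their mean rise above U still present at Week 0.

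Then
- never exposed: change = (U + E) − U = E
- previously exposed: change = (U + E) − (U + r) = E − r
- pooled: (1 − f)E + f(E − r) = **E − f·r**

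As a share of E this is 1 − f·(r/E). Both f and r/E are assumed here:

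| f | r = 0 | r = 0.25E | r = 0.5E | r = E | r = 1.5E |
|---|---|---|---|---|---|
| 0.25 | 100% | 94% | 88% | 75% | 63% |
| 0.50 | 100% | 88% | 75% | 50% | 25% |
| 0.75 | 100% | 81% | 63% | 25% | −13% |

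The last column is an extreme case. It takes the dose ratio 90/60 = 1.5 as the ratio of effects, with no washout and with every previously exposed patient leaving from the top arm.

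**When is the pooled change negative?** On treatment it needs f·r > E. At r = 1.5E that is f > 1/1.5 = 67%; at r ≤ E it cannot happen while f is below 1. At a visit where the drug effect has gone (E = 0), the pooled change is −f·r, which is negative for any r > 0. With f = 0.5 and r equal to half the on-treatment rise, it is −0.25 of that rise. Such visits fall within the endpoint, which covers the period after dosing, and Appendix 1 schedules coagulation at safety follow-up.

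**The case against.** The strongest reply is that washout may make the issue disappear. Section 1.2.2 reports that CRP and SAA returned to baseline by completion of GA29469 and that CRP rises in the Phase Ia study were transient. GA29469 completers leave at Day 134 and GA39925 completers at Week 30, after a maintenance phase on 60 µg/kg Q8W. For those later leavers, Section 3.3.1 describes the extension regimen as a doubling of exposure, not a step down. This stands for completers. It does not settle the case of patients leaving the larger parent (about 270 patients against 48) around Week 8, and it reports nothing on fibrinogen recovery.

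A reader might infer three stronger things that the documents do not support:
- **That Week 0 is an on-drug value for every previously treated patient.** The rule in Section 3.1.2 that the first extension dose "may not be administered less than 2 weeks after last dose of study drug in parent study" sets a minimum gap between doses. It does not say when the Week 0 blood sample was drawn. What can be said is that the value is post-exposure and may carry residual effect.
- **That the pooled on-treatment change will be zero or negative.** That needs a previously exposed share of at least two-thirds, even in the extreme column above.
- **That vital signs, lipids, liver tests and QTcF are biased in the same way.** No direction of drug effect is documented for them, and Phase Ia found no clinically significant vital-sign or ECG changes. The QTcF rule in Section 4.5.7 is an individual trigger for action at the site, not a pooled summary.

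It is also fair that Section 6.4 never writes change from baseline; the link comes from the Table 1 endpoint and the general rule in Section 6. No decision rule uses the mean change, and thromboembolism of Grade 2 or higher is captured directly as an event of special interest (Section 5.2.3).

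**Conclusion.** The point holds in a limited form. The stated baseline is post-exposure for part of the pool, no pre-exposure reference is named for laboratory change, and no split by parent treatment is required. For fibrinogen and CRP, any residual effect at Week 0 pulls the pooled on-treatment rise toward zero by f·r. Over the assumed f = 0.25 to 0.75 and r = 0 to E, between none and three-quarters of the rise is lost. At off-drug visits any residual effect gives a negative pooled change.

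This rests on an equal true rise in both groups and on a non-zero r. Residual effect is plausible for early GA39925 leavers but is not demonstrated. The correction is an inexpensive improvement to the main safety displays; it does not show that the planned result will be wrong.

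**What to change.** In Section 6.4:
1. State that Study Week 0 is the reference for laboratory change, and keep that display.
2. Present laboratory change, at least for fibrinogen and CRP, separately for patients first exposed to efmarodocokin alfa in this study and for those exposed in a parent study.
3. For the previously exposed, add change from the last value before their first efmarodocokin alfa dose in the parent study, where that value was collected. The documents do not confirm that GA39925 collected a pre-dose fibrinogen value, so availability must be checked.

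The third item is an added display, not a replacement reference for all safety measures. Leave the site-level QTcF rule in Section 4.5.7 as it is. Separately, reconcile the two statements of the 90 µg/kg interval in Section 3.3.1.

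The costs are programming to link parent-study records, which must wait for parent unblinding (Section 4.2), and smaller groups in each display. The added change also combines parent and extension periods. It includes any shift in disease activity over that time, which matters because fibrinogen and CRP are acute-phase proteins. It should be labelled accordingly.
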